## **5 STUDY EVALUATIONS AND MEASUREMENTS**

Variables that will be abstracted from medical charts:

 
○ Infant:
 
○ Name
 
○ Date of birth
 
○ Gestational age at birth
 
○ Birth weight
 
○ Race/ethnicity
 
○ Salivary Cortisol (post-salivary swab test)
 
	
 
○ Parent:
 
○ Name
 
○ Age
 
○ Race/ethnicity
 
○ Highest education completed (if available)
 
○ Salivary Cortisol (post salivary swab test)
 

--	--

#### *Parent Measures*

- Acceptability of Intervention Measure (AIM): A 12 item implementation outcome assessment designed to measure if the intervention is perceived as agreeable, palatable, or satisfactory.
- Feasibility of Intervention Measure (FIM): A 9 item implementation outcome assessment designed to measure the extent to which a new treatment can be successfully used or carried out.
- Patient-Reported Outcomes Measurement Information System (PROMIS) Adult Profile Short Form - Anxiety: The PROMIS Anxiety short form is a valid and reliable measurement tool used to assess self-reported fear, anxious misery, hyperarousal, and somatic symptoms related to arousal.
- Centers for Epidemiologic Studies Depression Scale (CESD): The CESD 20-item scale will be used.
- Edinburgh Postnatal Depression Scale (EPDS): A 10-item self-report questionnaire validated to detect change in depressive symptoms in mothers both during and after the postnatal period.
- Parenting Sense of Competence Scale (PSOC): This measure will be used to assess change in the parent's sense of competence in caring for their infant throughout the study period.

- Postnatal Attachment Questionnaire (PAQ): This questionnaire is associated with the Attachment Q-set (ASQ), an observational assessment of infant-parent bonding, and will serve as a measure of the parent emotional component of infant-parent bonding in the follow-up stage of the study period.
- Salivary Cortisol: Salivary cortisol is a biomarker for stress. Salivary cortisol concentrations (ng/dl) may be used to understand the mechanism by which TEMPO impacts physiological stress states. The PI or research coordinator will swab the parent's buccal mucosa immediately pre- and post-massage at the first massage education session.
- Parent Interview: The parent who performed the study intervention will be interviewed at the first follow-up visit and the 12-month follow-up visit to obtain their insights on the feasibility, acceptability and perceived benefit of TEMPO. The PI or study coordinator elicit their feedback on program materials, intervention components, and factors that influenced whether they were able to continue the protocol at various time points post-discharge. For example: what they liked or disliked about the program, how often they did massage and for how long, did they find the massage easy to do on an ongoing basis, do they have suggestions to improve feasibility? We will also ask about willingness to have participated in this study if it were a randomized trial. This information will be critical to develop the planned trial (Aim 1 and 2). For example, should a parent not be willing to be randomized, the trial may need to randomize at some level other than individual infants/parents (e.g., hospital or a waitlist control condition).

#### *Infant Measures*

- Salivary Cortisol: Salivary cortisol will be collected by PI via buccal swab immediately pre- and post-massage at the first massage education session.
- Carey Temperament Scales (CTS): This questionnaire assesses Infant temperament to better understand if infant temperament may be influenced by massage and is associated with parent-infant bonding.
- Bayley Scales of Infant Motor Development-III (BSID-III): A standardized assessment provided by a developmental specialist (physical or occupational therapist in our study) to evaluate cognitive development, expressive and receptive language, and fine and gross motor development in children between the ages of 1 month and 42 months.

### **5.1 Safety Evaluations**

The infant will be monitored for safety throughout all PT sessions. With the assistance of the bedside nurse, vital signs will be monitored continuously (heart rate, oxygen saturation, and respiratory rate) during all massage and physical therapy interventions. The massage or PTIs will be stopped if the infant's heart rate exceeds 200 beats per minute, if the infant's oxygen saturation drops <90%, or respiratory rate exceeds 90 breaths per minute without spontaneous recovery or response to strategies employed by the PT or nurse to resolve. Additionally, the PT will monitor infant behavioral-motor cues for signs of overstimulation or stress during massage and PTIs in order to promote a positive experience for the infant and parent. If the infant demonstrates any of these negative responses during massage or PTIs, then the PT will adjust the treatment session accordingly to focus on developmental support that the infant can tolerate, while continuing to educate the parent about their infant's cues and behavior.

Prior to the parent education for massage session, the PT will test a small area of the infant's skin (likely on the lower leg or back) to assess any negative skin reaction to Aquaphor, the medium used for massage. If after 24 hours of monitoring, the infant does not develop skin irritation, then the PT will proceed with an introductory massage session. If the infant has a skin reaction to Aquaphor, then the PT will determine an alternative medium for massage in consultation with the medical team and the skin care nurse. Infant massage will first be administered by the PT to determine the infant's tolerance prior to the parent education for massage session.

The study team will generate Study Reports for the Independent Monitor and will provide information on the following study parameters: screened and enrolled parent-infant dyads, unanticipated, serious adverse events, missed study visits and dyads that are lost to follow-up.

## 6 STATISTICAL CONSIDERATIONS

### 6.1 Primary Objectives

No hypothesis tests will be performed in this study. The primary goal of this project is to test feasibility and acceptability of the TEMPO program and study protocol (Aim 1). As such, the analysis plan will not focus on inferential statistics but on measures of feasibility identified in the NCCIH's *Framework for Developing and Testing Mind and Body Interventions* (<https://nccih.nih.gov/grants/mindbody/framework>):

- Recruitment: Percentage of eligible infant-parent dyads who enroll in the study (Goal  $\geq 55\%$ )
- Willingness to be randomized: Percentage of enrolled parents who, in interviews, report they would agree to be randomized (Goal  $\geq 70\%$ )
- TEMPO delivered per protocol: Percentage of enrolled parents who complete all TEMPO components per protocol (Goal  $\geq 70\%$ ) and weekly and bi-weekly reporting of physical therapy interventions (goal  $\geq 50\%$ ).
- Retention: Percentage of enrolled parents who are retained in the study at 12 months (Goal  $\geq 70\%$ ), reasons for attrition for those who do not complete the protocol
- Complete data collection: Percentage of enrolled parents who complete data collection, including interviews (Goal  $\geq 70\%$ )
- Adherence: Percentage of enrolled parents who complete at least 2-3x/week during hospitalization and 2-3x/week in-home PTIs as noted on the parent log or survey (Goal  $\geq 70\%$ )
- Acceptability and Feasibility of TEMPO: Percentage of parents who rate acceptability and feasibility as 4/5 or 5/5 using the Acceptability of Intervention Measure and the Feasibility of Intervention Measure (Goal  $\geq 70\%$ )
- Acceptability of the Protocol: A structured interview guide will be followed by the PI or research coordinator. Interviews will be audio recorded and transcribed by a confidential online service. All audio files will be stored and transmitted using TLS 1.2 encryption for a high level of security. Interviews will be coded by the PI for content and qualitative analysis to derive themes. (Aim 1 and 2)

### 6.2 Secondary Objectives

Additionally, we plan to estimate the means and standard deviations as the basis for sample size calculations using the following measures for future clinical trials.

#### *Parent Measures*

- PROMIS Adult Short Form - Anxiety
- Centers for Epidemiologic Studies Depression Scale (CESD)
- Edinburgh Postnatal Depression Scale (EPDS)
- Parenting Sense of Competence Scale (PSOC)
- Postnatal Attachment Questionnaire (PAQ)
- Salivary Cortisol
- Parent Interview

#### *Infant Measures*

- Salivary Cortisol

- Carey Temperament Scales (CTS)
- Bayley Scales of Infant Motor Development-III (BSID-III)

### 6.3 Statistical Methods

In addition to the analysis plan above, we will calculate the mean and standard deviation of each potential outcome measure to estimate the sample size required for a randomized trial. All statistical estimates of population parameters will be tabulated along with corresponding confidence intervals (CIs) (Aim 1). We will combine that information with what we learn from parent interviews as the basis for selecting primary and secondary outcomes for future randomized trials to evaluate TEMPO (Aim 2).

Although validated outcome measures will be collected in this pilot study in order to refine the TEMPO protocol for future study, these variables will not be incorporated in the statistical analyses of outcomes. Collection of the validated measures will also be used to select a sample size for a full study (Aim 3). We anticipate this data will be used to develop estimates of correlations among repeated measures, means and standard deviations. Point-estimates of the means, standard deviations, and correlations will be tabulated along with corresponding confidence intervals (Aim 3).

### 6.4 Interim Analysis

Apart from safety monitoring, no interim analyses will be performed.

Data type	Frequency of review	Reviewer
Subject accrual (including compliance with protocol enrollment criteria)	Every 2 weeks	PI
	Quarterly	Independent Monitor
Status of all enrolled subjects, as of date of reporting	Monthly	PI
	Quarterly	Independent Monitor
Data entry quality control checks on 20% of charts	Quarterly	PI
Adherence data regarding study visits and intervention	Monthly	PI
	Quarterly	Independent Monitor
AEs	Monthly, within 24 hours	PI
	Quarterly, within 24 hours	Independent Monitor
	Annually	NCCIH
SAEs (unexpected and related)	Per occurrence	PI, Independent Monitor NIH/NCCIH

Unanticipated Problems	Monthly	PI
	Per Policy	IRB, NCCIH

## 7 STUDY INTERVENTION

- **Early Parent Education Session:** Initiated within 3 weeks of infant birth. The PT will educate the parent about the importance of infant positioning, the impact of prematurity on the motor and sensory systems, and how to read and respond to infant behavioral-motor cues using a written pamphlet with pictures to supplement the verbal education lasting about 30 minutes.
- **Weekly Parent Education Sessions <34 weeks:** Following the initial parent education session, the PT will hold weekly parent education sessions, ideally at the time of therapy. When the infant is this young (<34 weeks gestation), PT intervention and education will focus on infant behavioral-motor cues, reading/response to infant cues, positioning strategies/concerns, and developmentally appropriate stimulation of the infant. If the parent is not available for all therapy sessions, then the parent will receive a weekly update about their infant's progress face-to-face and/or via video chat.
- **Infant Massage Parent Education Sessions:** Parent-administered infant massage will be incorporated into the therapy plan of care as soon as the infant's medical provider determines that the infant is physiologically stable and can tolerate massage. At a minimum, the therapist will teach massage for the back or lower extremities over 2 parent education sessions – one early session in the isolette (if necessary) and one later session out of the isolette. The therapist will demonstrate massage strokes on a doll using verbal cues to guide the parent while the parent administers massage on the infant. An instructional massage pamphlet will be provided. The massage intervention is comprised of moderately firm effleurage strokes on the extremities for periods of 10-20 minutes followed by gentle passive muscle elongation. Use of upper or lower body swaddle, pacifier, and room darkening may be necessary to achieve positive infant responses during massage.
- **Visits 11+: Weekly Parent Education Sessions >34 weeks:** Weekly parent education once the infant is >34 weeks will begin to incorporate hands-on developmental play activities, introduction to visual engagement, and postural control practice in variety of positions that the infant tolerates. Additionally, the PT and parent may choose to review massage at these visits. If the parent is not available for all therapy sessions, then the parent will receive a weekly update about their infant's progress face-to-face and/or via video chat.
- **Discharge Parent Education Session:** Within the week of hospital discharge, the PT will schedule a face-to-face parent education session lasting about 30 minutes to review age-appropriate developmental play activities for home and review infant massage. A supplemental handout and therapist email and pager information will be provided.
  - **Additional Physical Therapy Intervention Description:** Age appropriate physical therapy interventions and developmental play activities will be taught to parents during the hospital stay at weekly visits and at the discharge parent education session. These activities may include but are not limited to: Prone positioning to develop head, neck, and shoulder strength, supine play activities like patty-cake and leg bicycles to promote flexion of the trunk and extremities against gravity, visual tracking activities to promote symmetrical movement of the neck/head, and supported sitting activities in the parent's lap to promote postural control.
- **Parent Education Post-Discharge:** The PT will call the parent within 2 weeks of discharge to follow up about discharge education and massage. During this phone call, the PT will review the home program and massage

techniques. The PT will also answer any parent questions. Therapist email and pager information will be provided.

- **2 Month Follow-up Massage Review Session:** At the standard of care 2-month follow-up appointment with the multidisciplinary neonatology team, the PT will provide a gross motor screening assessment and education. In addition, as part of the TEMPO program, a PT will facilitate a parent-administered infant massage session to provide an opportunity for parent to receive feedback on technique from the PT. This session will address any safety concerns, infant changes, and parent questions.
- **Bi-weekly emails:** The PT will continue to send bi-weekly emails with developmental play activity and massage reminders until the 12 month follow-up appointment.
- **12 Month Follow-up Appointment:** At the standard of care 12 month follow-up appointment with the multidisciplinary neonatology team, the PT will administer a standardized assessment of gross and fine motor skills (Bayley Scales of Infant Development 3).

## 8 SAFETY MANAGEMENT

This study will be stopped prior to its completion if: (1) the intervention is associated with AEs that call into question the safety of the intervention in infants <28 weeks gestational age; (2) significantly lower study recruitment or retention than expected that will impact the ability to evaluate feasibility of TEMPO.

### Definitions

#### Adverse Event (AE)

An adverse event (AE) is any untoward medical occurrence in a subject during participation in the clinical study or with use of the experimental agent being studied. An adverse finding can include a sign, symptom, abnormal assessment (laboratory test value, vital signs, electrocardiogram finding, etc.), or any combination of these regardless of relationship to participation in the study.

#### Unanticipated Problems (UP)

The Office for Human Research Protections (OHRP) considers unanticipated problems involving risks to subjects or others to include, in general, any incident, experience, or outcome that meets **all** of the following criteria:

- Unexpected in terms of nature, severity, or frequency given (a) the research procedures that are described in the protocol-related documents, such as the IRB-approved research protocol and informed consent document; and (b) the characteristics of the subject population being studied;
- Related or possibly related to participation in the research (“possibly related” means there is a reasonable possibility that the incident, experience, or outcome may have been caused by the procedures involved in the research); and
- Suggests that the research places subjects or others at a greater risk of harm (including physical, psychological, economic, or social harm) than was previously known or recognized.

#### Serious Adverse Event (SAE)

A serious adverse event (SAE) is one that meets one or more of the following criteria:

- Results in death
- Is life-threatening (places the subject at immediate risk of death from the event as it occurred)
- Results in inpatient hospitalization or prolongation of existing hospitalization
- Results in a persistent or significant disability or incapacity
- Results in a congenital anomaly or birth defect

An important medical event that may not result in death, be life threatening, or require hospitalization may be considered an SAE when, based upon appropriate medical judgment, the event may jeopardize the subject and may require medical or surgical intervention to prevent one of the outcomes listed in this definition.

#### Time Period and Frequency for Event Assessment and Follow-Up

An independent monitor has been identified to review enrollment, UPs, and AEs. The study team will send the independent monitor a report on enrollment every 4 months, with the expectation that the independent monitor will provide input on enrollment within 30 days. UPs and AEs will be reported to the independent monitor within 24 hours with the expectation that the independent monitor will provide input on UPs and/or AEs within 5 days.

#### Characteristics of an Adverse Event

##### Relationship to Study Intervention

The potential event relationship to the study intervention and/or participation is assessed by the site investigator. A comprehensive scale in common use to categorize an event is:

- *Definitely Related*: The adverse event is clearly related to the investigational agent/procedure – i.e. an event that follows a reasonable temporal sequence from administration of the study intervention, follows a known or expected response pattern to the suspected intervention, that is confirmed by improvement on stopping and reappearance of the event on repeated exposure and that could not be reasonably explained by the known characteristics of the subject's clinical state.
- *Possibly Related*: An adverse event that follows a reasonable temporal sequence from administration of the study intervention follows a known or expected response pattern to the suspected intervention, but that could readily have been produced by a number of other factors.
- *Not Related*: The adverse event is clearly not related to the investigational agent/procedure - i.e. another cause of the event is most plausible; and/or a clinically plausible temporal sequence is inconsistent with the onset of the event and the study intervention and/or a causal relationship is considered biologically implausible.

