#### Adverse Event Reporting

SAEs that are unanticipated, serious, and possibly related to the study intervention will be reported to the Independent Monitor, IRB, and NCCIH in accordance with requirements.

- Unexpected fatal or life-threatening AEs related to the intervention will be reported to the NCCIH Program Officer, and Independent Safety Monitor(s) within 3 days of the investigator becoming aware of the event. Other serious and unexpected AEs related to the intervention will be reported within 7 days.
- Anticipated or unrelated SAEs will be handled in a less urgent manner but will be reported to the Independent Safety Monitor(s), IRB, and other oversight organizations in accordance with their requirements, and will be reported to NCCIH on an annual basis.
- All other AEs documented during the course of the trial will be reported to NCCIH on an annual basis by way of inclusion in the annual report and in the annual AE summary which will be provided to NCCIH and to the Independent Monitors. The Independent Safety Monitor(s) Report will state that all AEs have been reviewed.

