#### Halting Rules

An infant may no longer participate in the study under any of the following circumstances:

- The medical condition of the infant deteriorates and the medical team no longer recommends PT or massage
- The infant experiences a severe AE or SAE related to the intervention
- The Parent is no longer interested in participating

In the event that an infant has an AE related to massage medium (Aquaphor), then massage will be performed without the medium or with a medium approved by the medical team once the skin has healed.

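### The causality scale in section 8 has no class for a plausible event of a new kind, and its *possibly related* conflicts with the definition used for unanticipated problems

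*Combined protocol and SAP*

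**What the plan says.** **The scale.** Section 8, Relationship to Study Intervention, gives three classes, rated by the site investigator.

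- *Definitely Related*: among other conditions, the event "follows a known or expected response pattern to the suspected intervention, that is confirmed by improvement on stopping" and reappears on re-exposure.
- *Possibly Related*: the event has a reasonable time sequence and "follows a known or expected response pattern to the suspected intervention, but that could readily have been produced by a number of other factors"; this is the weaker of the two related classes.
- *Not Related*: the event is clearly unrelated, in that "another cause of the event is most plausible; and/or a clinically plausible temporal sequence is inconsistent with the onset of the event", or a causal link is biologically implausible.

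No other scale is given for rating AE causality.

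**Expectedness.** Section 8, Expectedness of SAEs, makes this a separate judgement by the PI, the infant's medical team and the independent monitor. It rests on the features of the event and on risks already reported in the literature.

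**The other definition.** Section 8, Unanticipated Problems (UP), uses the term possibly related to mean that "there is a reasonable possibility that the incident, experience, or outcome may have been caused by the procedures involved in the research". It has no pattern condition.

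**What depends on the rating.** The table in section 6.4 gives per-occurrence review to SAEs that are both unexpected and related. Section 8, Adverse Event Reporting, says "Unexpected fatal or life-threatening AEs related to the intervention will be reported to the NCCIH Program Officer" and the safety monitors within 3 days, and sets 7 days for other serious, unexpected, related AEs. SAEs that are anticipated or unrelated, and all remaining AEs, go to NCCIH annually. Section 4.4 and Halting Rules also use the term: "The infant experiences a severe AE or SAE related to the intervention" is one ground on which an infant may leave the study.

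**The concern.** Whether the intervention may have caused an event, and whether that kind of event was foreseen, are two different questions. The pattern condition merges them: before an event can be called even possibly related, it must look like something already known or expected. Yet the fast AE reports are reserved for events that are related and unexpected. For an event unexpected in nature, the scale withholds the first half of that condition because of the second.

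This matters more here than in a well-studied setting. Section 1.1 describes infants below 28 weeks as a population not covered by earlier massage research. Expectedness of SAEs says, more cautiously, that massage has been studied less extensively in them. On either statement few response patterns are established, and an event of a new kind is one that safety monitoring most needs to classify properly.

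The protocol also uses one term with two meanings. The same event can be possibly related when considered as a UP and fail that class when rated as an AE. No text says which meaning governs the opening sentence of Adverse Event Reporting, which also uses the term.

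**Working it through.** No arithmetic applies. The check takes one test event through each rule.

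**Test event (assumed).** A serious event after massage, with plausible timing, of a kind not previously described with massage, with no other cause more plausible and no biological implausibility.

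**Step 1: the causality scale.**

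| Class | Condition that decides it | Met? |
|---|---|---|
| *Definitely Related* | known or expected pattern | No |
| *Possibly Related* | known or expected pattern | No |
| *Not Related* | better cause, inconsistent timing, or implausible mechanism | No |

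The event fits 0 of 3 classes, so the scale is not exhaustive.

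**Step 2: overlap.** Now take an event of known pattern and plausible timing for which "another cause of the event is most plausible; and/or" nothing else in *Not Related* is needed. Such an event could also readily have come from other factors, so it meets *Possibly Related* as well. The classes are not exclusive either.

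**Step 3: the reporting rules applied to the test event.**

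| Rule | Needs | Reached? |
|---|---|---|
| Section 6.4, per occurrence | unexpected and related | Not on this scale |
| Adverse Event Reporting, 3 days | unexpected, fatal or life-threatening, related | Not on this scale |
| Adverse Event Reporting, 7 days | serious, unexpected, related | Not on this scale |
| Unanticipated Problem Reporting, 24 hours to IRB, monitor and NCCIH | a UP that is an SAE | Yes, if all three UP criteria are judged met |
| Time Period and Frequency for Event Assessment and Follow-Up, 24 hours to the monitor | any AE or UP | Yes |

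**Step 4: the UP route.** The test event can be unexpected in nature and, under the UP definition, possibly related. The third criterion is that it suggests greater risk than was previously recognised. If that is judged met, the 24-hour route applies, and it is faster than 3 or 7 days.

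**Step 5: how far the unexpected-and-related class shrinks.** The UP definition counts severity and frequency, as well as nature, as ways of being unexpected. An event of known pattern but unexpected severity or frequency can still be rated related and also be unexpected. The class is narrowed, not emptied.

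**The case against.** The strongest reply is that the protocol has other routes. The UP definition has no pattern condition, and a serious event of a new kind would ordinarily also suggest increased risk, so NCCIH would hear within 24 hours. The monitor receives every AE within 24 hours and is expected to respond within 5 days. Reporting Procedures separately requires information suggesting new or increased risk to be reported within 7 calendar days, with no causality grade. All of this stands, and it limits the point.

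It does not remove it. A UP must meet all three criteria, and nothing tells an investigator who has just rated an event on the AE scale to rate it again under the UP definition.

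Four stronger readings are tempting, and the documents do not support them.

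- *NCCIH would learn of a new kind of SAE only in the annual report.* This overlooks the 24-hour UP route.
- *The scale pushes new events into Not Related and biases the count of related AEs downward.* Novelty alone meets none of that class's conditions, so the event is left without a class. No table of related AEs is specified; Data Monitoring in section 9 asks for a list and summary of AEs.
- *Definitely Related is out of reach because it needs an event "that is confirmed by improvement on stopping and reappearance of the event on repeated exposure" while the participation rule may remove the infant.* No report depends on that class, *Possibly Related* remains available for known patterns, and an event could recur before participation ends.
- *Infants harmed in a new way would have to stay in the study.* Section 4.4 and Halting Rules also allow participation to end when the infant deteriorates and the medical team no longer recommends therapy, whatever the cause.

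**Conclusion.** The scale is wrong as written, in a limited but safety-relevant way. Both of its related classes carry a condition that belongs to expectedness, and the weaker one contradicts the protocol's own definition of the same term. A plausible event of a new kind has no class and, rated on this scale, cannot meet the section 6.4 trigger or the 3- and 7-day rules.

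The exposure is confined to the AE causality rating itself and to those reports for events not also handled as UPs. The documents give no basis for estimating how many events that would be. The conclusion assumes that the scale is applied literally. An investigator who reads the opening sentence of Adverse Event Reporting in the UP sense would report such an event, but the text does not tell them to.

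**What to change.** 1. In Relationship to Study Intervention, replace the pattern condition in *Possibly Related* with the reasonable-possibility wording already used for UPs.
2. Leave expectedness to the review described under Expectedness of SAEs.
3. Redraw the class boundaries so that every event falls into exactly one class.
4. For reporting under section 6.4 and Adverse Event Reporting, state that related includes possibly related. The opening sentence of Adverse Event Reporting already implies this.
5. Ask the sponsor to reconcile the meaning of related in section 4.4 and Halting Rules with the revised scale. Who should leave the study is a clinical decision, and no participation rule is proposed here.

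The cost is amendment wording that draws on a definition already in the protocol. The downside is that somewhat more AEs will be classed as possibly related and reported early.
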